5.1.1 Retesting During Screening or Lead-in Period

Retesting of laboratory parameters and/or other assessments within any single Screening or Lead-in period will be permitted (in addition to any parameters that require a confirmatory value).

Any new result will override the previous result (ie, the most current result prior to Randomization) and is the value by which study inclusion will be assessed as it represents the subject's most current, clinical state.

5.2 Study Materials

The site will provide all required materials for the tests performed locally (ie, relevant clinical laboratory tests). The site will have available a well-calibrated scale for recording height and body weight, a 12-lead ECG machine, and a calibrated sphygmomanometer and thermometer for vital signs assessments. A current and fully-stocked advanced cardiac life support cart will be immediately available on the premises. The site will have a refrigerated centrifuge, a monitored and alarmed refrigerator, and freezer (-20°C or below), as well as containers and dry ice for storage of blood and urine samples. The site will provide all materials required for accurate source documentation of study activities and for housing the subjects during the study. The site will have the proper equipment for the infusion of ulocuplumab including an infusion pump.

The site will also provide premedication for infusion reaction.

BMS will provide a BMS-approved protocol and any amendments or administrative letters (if required), investigator brochure and procedure manuals. Case report forms (electronic or hard copy) will be provided by BMS. BMS/The Central Laboratory will provide labels and tubes for the collection of blood samples for PK and immunogenicity analysis.

5.3 Safety Assessments

The study is divided into periods with associated evaluations and procedures that must be performed at specific timepoints. The Time and Events Schedules ([Table 5.1-1](#), [Table 5.1-2](#), and [Table 5.1-3](#)) summarizes the frequency and timing of these evaluations and procedures.

The following safety assessments will be performed during the study for all subjects: vital sign measurements, clinical laboratory tests, bone marrow tests, ECOG performance status evaluations ([Appendix 4](#)), physical examinations/measurements, ECGs (12-lead), concomitant medications, transfusions, and the incidence and severity of AEs.

The incidence of observed AEs will be tabulated and reviewed for potential significance and clinical importance.

Subjects will be evaluated for safety if they have received at least 1 dose of study drug. Toxicity assessments will be continuous during the treatment phase. During the safety follow-up phase (Follow-up visit X01, Table 5.1-3), toxicity assessments should be done in person. Once subjects reach the survival follow-up phase either in person or documented telephone calls/emails to assess the subject's status are acceptable.

5.3.1 Evaluation and Reporting of Dose Limiting Toxicity (DLT)

DLT will be determined based on the incidence and intensity of AEs occurring in Cycle 1 using NCI CTCAE v4.03. DLT(s) will be defined as any of the following events which are attributed (ie, judged to be related) to the ulocuplumab. AEs that are judged by the investigator to be solely attributed to cytarabine (based upon clinical experience and the known toxicities of these agents), will not be considered DLTs. AEs should be evaluated carefully by the investigator prior to attribution. AEs may be attributed to ulocuplumab if, in the judgment of the investigator, the nature, severity, or timing is unexpected from LDAC (cytarabine). If the events listed below occur, these events will be discussed by the investigator and the BMS Medical Monitor to determine whether they qualify as DLT or not considering its clinical significance. Study drugs (ulocuplumab and LDAC (cytarabine)) will be permanently discontinued for any subject that experiences a DLT.

DLT is defined as:

- Any ulocuplumab related grade ≥ 3 nonhematologic toxicity not due to the underlying disease occurring during Cycle 1.
- Marrow that does not adequately recover within 8 weeks from the last study drug administration ($< 10\%$ cellularity with $< 10\%$ blasts) will be considered a hematologic DLT if related to ulocuplumab.
- Any ulocuplumab related grade 4 (life-threatening) hematologic toxicity lasting > 14 days.

The following will not be considered a DLT:

- Grade 3 nausea or vomiting that are controllable with medications
- Grade 3 neutropenic fevers or infections
- Grade ≥ 3 tumor lysis syndrome
- Grade ≥ 3 metabolic derangements attributed to antifungal medications or tumor lysis that corrected with IV or oral supplementation
- Grade 3 stomatitis that resolves within 7 days of discontinuation of chemotherapy
- Grade ≥ 3 hypercholesterolemia
- Grade 3 hyperbilirubinemia or transaminitis that resolves to below grade 2 within 14 days
- Grade 3 infusion reactions.

Subjects will be considered to have completed a DLT assessment period if they complete all doses of ulocuplumab and cytarabine for Cycle 1 (28 days). This does not apply to subjects who experience DLTs.

5.3.2 **Laboratory Test Assessments**

A local laboratory will perform the analyses including C-Reactive Protein testing and will provide reference ranges for these tests.

Results of local clinical laboratory tests must be reviewed prior to infusion.

The following clinical laboratory tests will be performed:

Hematology

Hemoglobin

Hematocrit

Total leukocyte count (and differential)

- Automated differentials are acceptable, absolute counts reported and/or percentages of circulating tumor cells (if any), neutrophils, lymphocytes, monocytes, basophils, eosinophils.

Platelet count

Blast percentage

Serum Chemistry

Aspartate aminotransferase (AST)

Alanine aminotransferase (ALT)

Total bilirubin

Direct bilirubin

Alkaline phosphatase

Lactate dehydrogenase

Creatinine

Blood Urea Nitrogen or Urea

Uric acid

Lipase

Amylase

Glucose

Total Protein

Albumin

Sodium

Potassium

Chloride

Calcium

Phosphorus

Creatine kinase

Urinalysis

Protein

Glucose

Blood

Leukocyte esterase

Microscopic examination of the sediment including WBC/high power field (HPF), red blood cell (RBC)/HPF if blood, protein or leukocytes esterase are positive on the dipstick

Pregnancy Test (WOCBP only); urinalysis or serum

Serology

Hepatitis C antibody

Hepatitis B surface antigen

Hepatitis B core antibody

HIV antibody

Other:

C-Reactive Protein

Results of all laboratory tests required by this protocol must be provided to BMS, either recorded on the laboratory pages of the CRF or by another mechanism as agreed upon between the investigator and BMS (eg, provided electronically). If the units of a test result differ from those printed on the CRF, the recorded laboratory values must specify the correct units. Any abnormal laboratory test result considered clinically significant by the investigator must be recorded on the appropriate AE page of the CRF (see [Section 6.3](#), Laboratory Test Abnormalities).

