3 INVESTIGATIONAL PLAN

3.1 Study Design and Duration

In the escalation phase, this was a Phase 1, open-label study to assess the safety and tolerability of ulocuplumab in subjects with AML. The study consisted of 3 periods: Screening (up to 28 days), Treatment (28 days/cycle) and Follow-up (at least 30 days following the end of treatment visit). Escalation phase subjects will be followed for overall survival (OS) for at least 2 years. The dose of ulocuplumab chosen to be explored in the escalation cohort of this study (600 mg and 800 mg) was selected based on the results from a Phase 1 study (CA212001).

Based upon the CA212016 escalation cohort results, the protocol is revised to include an exploratory, non-comparative open-label Phase 2 expansion cohort of up to approximately an additional 120 AML subjects. Expansion cohort subjects will be randomized to 1 of 3 treatment arms: LDAC alone or either 800 mg or 1000 mg ulocuplumab in combination with LDAC 20 mg BID (Figure 3.1-2). Escalation cohort subjects who are continuing treatment will continue at their assigned dose. In the expansion cohort, randomization will be suspended in the ulocuplumab 1000 mg arm while safety data from the first 6 subjects in this arm are evaluated for DLTs. For the escalation and expansion cohorts, DLTs and all other toxicities were defined and evaluated using the National Cancer Institute Common Terminology Criteria for Adverse Events Version 4.03 (NCI CTCAE v4.03). DLTs were defined based upon events that were considered to be related to ulocuplumab in combination with LDAC and that occurred during the first cycle of drug administration (28 days).

The Screening Period is defined as the 28 days following initiation of screening assessments and before administration of the first dose of any study drug, during which subjects are evaluated for study eligibility.

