4.6.1.2 Dose Modifications, Infusion Delays and Missed Doses

No subject will be permitted dose modifications of ulocuplumab and LDAC during Cycle 1. After Cycle 1, if the dose of ulocuplumab or LDAC is interrupted or discontinued, the treatment with the other drug may continue as scheduled. Each cycle is 28 days. Missed doses should be skipped, not delayed, if not given within the allowed window. Please consult the BMS Medical Monitor for any questions regarding dose interruption or study therapy discontinuation.

Ulocuplumab:

The study allows dose delays of ulocuplumab but does not allow dose reductions or escalations throughout the treatment period. Dose delays of ulocuplumab are not permitted during Cycle 1.

Criteria to start a new cycle:

- After Cycle 1, every effort should be made to give the first dose of ulocuplumab and LDAC in Cycle 2 within 7 days of the end of the previous cycle in order to maximize dose intensity. Dose delays up to a maximum of 28 days are allowable for grade 3 or 4 non-hematologic toxicities, with resumption of dosing when resolved to grade 1 or less. This does not include situations when the subject's marrow has not yet recovered from effects of chemotherapy from a previous cycle. A dose delay of up to a maximum of 42 days is allowable for prolonged myelosuppression defined by ANC $\leq 500/\mu\text{L}$ or platelet count $\leq 10 \times 10^9/\text{L}$ in a normal bone marrow with $\leq 5\%$ blasts and no evidence of disease or dysplasia .
- At Cycle 3 and beyond, dose delay for recovery from myelosuppression (or other AE) up to a maximum of 56 days is allowed for grade 3 or 4 non-hematologic toxicities, or prolonged myelosuppression as defined above.

Once a treatment cycle is begun:

- For Cycles 1 and 2, a window of -1 to +3 days is permitted for ulocuplumab administration on Days 8 and 15.
- Beginning with Cycle 3 and beyond, a window of -1 to +7 days is permitted for ulocuplumab administration on Day 8.
- Infusions of ulocuplumab that cannot be administered in that window period will be considered a missed dose, and the subject should come in for their next, regularly scheduled visit relative to Day 1 of the next cycle.

A subject should be discontinued from ulocuplumab if they do not receive a dose within 56 days of the last ulocuplumab dose.

Table 4.6.1.2-1: Dose Delay and Discontinuation Criteria for Ulocuplumab-related Adverse Events

Adverse Event	Action

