8.5 Interim Analyses

For the dose expansion cohort, an interim assessment of safety will be assessed by Sponsor or designee on the first 6 patients treated on the 1000 mg ulocuplumab/LDAC combination arm. These must have had an opportunity for at least 28 days of follow-up. The review will be based all available safety data including DLTs reported during the first 28 days of follow-up. Randomization to the 1000 mg ulocuplumab combination arm will be suspended until the safety review is complete. Randomization to the other 2 arms will continue on a 1:1 basis until a decision is reached to resume randomization to all 3 arms.

In addition, an interim analysis of efficacy and safety will be conducted when 60 patients (i.e., 50% of the sample size) will have had an opportunity for 2 months of treatment and follow-up.

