2 STUDY DESCRIPTION

2.1 Schedule of Analyses

Phase 1 (escalation cohort) has previously been analyzed; the original SAP is attached as an appendix to this document. This SAP applies similar methodology to Phase 2 (expansion cohort), the following analyses of which are planned:

Table 1: Planned Analyses of Expansion Cohort

Meeting/Format	Timing	Purpose
DMC Interim #1	When the first 6 subjects in the ulocuplumab 1000mg arm have had opportunity for 28 days of follow-up	Review of all available safety data, especially pertaining to the ulocuplumab 1000mg dose; results will be available for review by BMS also
DMC Interim #2	When around 60 subjects (20 per treatment arm) have completed 2 months of treatment and follow-up	See DMC Charter for additional details; results will be available for review by BMS also
DMC Interim #3 (SAE only)	About 12 months after interim #2	See DMC Charter for additional details
Final analysis	After all patients have had opportunity for 6 months of follow-up	For final report (CSR)
DMC final meeting	When 100% of subjects have completed or discontinued from all study drugs	Review all safety data for the proposed treatment regimen and provide insight for potential future trials
Study completion analysis	At completion of study (subject follow-up complete)	Review mature OS data

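### The Day 28 gate for the 1000 mg arm can be passed before two listed hematologic DLTs can be confirmed, with no rule for a DLT confirmed later; the 33% limit should also be a count out of 6

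*Protocol*

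**What the plan says.** **The gate.** Protocol 3.1 and SAP 2.2 suspend randomization to ulocuplumab 1000 mg while the first six subjects are evaluated for DLTs. The arm resumes if at most 33% have a DLT and accrues no further if more than 33% do. Neither document turns this into a number out of six.

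**When it is decided.** Protocol 8.5 says of the six: "These must have had an opportunity for at least 28 days of follow-up". The review covers "all available safety data including DLTs reported during the first 28 days of follow-up". SAP 2.1 places DMC Interim #1 at the same point: "When the first 6 subjects in the ulocuplumab 1000mg arm have had opportunity for 28 days of follow-up".

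**What counts as a DLT.** Protocol 5.3.1 opens with "DLT will be determined based on the incidence and intensity of AEs occurring in Cycle 1". Protocol 3.1 and SAP 2.2 likewise confine DLTs to the 28-day first cycle. The list in 5.3.1 nevertheless contains two duration-based hematologic criteria, both of which must be related to ulocuplumab:
- "Marrow that does not adequately recover within 8 weeks from the last study drug administration" (less than 10% cellularity with less than 10% blasts);
- "Any ulocuplumab related grade 4 (life-threatening) hematologic toxicity lasting > 14 days".

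**Delays after Cycle 1.** Protocol 4.6.1.2 says of starting Cycle 2: "A dose delay of up to a maximum of 42 days is allowable for prolonged myelosuppression".

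**The concern.** The gate is decided on a proportion of subjects with a DLT, but two of the listed DLTs need elapsed time that a Day 28 review may not contain. A subject whose marrow is failing at Day 28 is not yet a DLT under the 8-week criterion. The arm could reopen on a count that later proves too low, and no rule says what to do then.

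In these documents this is the only numeric rule that governs further accrual at 1000 mg, a dose not given in the escalation cohort (600 and 800 mg). Protocol 1.5 names hematologic toxicity as a possibility, and that is the kind of event the count can omit.

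The limit itself adds a smaller problem. With six subjects, the attainable rate nearest to 33% is 2 of 6, or 33.3%. The sponsor should confirm that closing the arm at 2 of 6 is what it wants.

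**Working it through.** The plan states no error rate or operating characteristic for this gate, so there is no figure of its own to reproduce. The DLT rates used in steps 4 and 5 are assumptions.

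**1. Marrow criterion (8 weeks = 56 days).** Earliest study day = day of last study drug + 56, if no Cycle 2 drug is given.
- Dosing stopped after Day 1: 1 + 56 = Day 57.
- Third Cycle 1 infusion on Day 15, window -1 to +3 days (Protocol 4.6.1.2): 14 + 56 = Day 70; 15 + 56 = Day 71; 18 + 56 = Day 74.

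These dates fall 29 to 46 days after Day 28. A subject who starts Cycle 2 restarts the clock, because it runs from the last study drug.

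**2. Grade 4 criterion (more than 14 days).** Days from onset to Day 28, counted inclusively:
- onset Day 13: 16 days; Day 14: 15 days; Day 15: 14 days.

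Counted as elapsed days these are 15, 14 and 13. On either count, onset on or after Day 15 cannot exceed 14 days by Day 28. Day 15 is also the scheduled day of the third infusion.

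**3. Late suppression is provided for.** The permitted Cycle 2 delay reaches Day 28 + 42 = Day 70.

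**4. When one late DLT would change the decision.** Suppose exactly one of the six has a DLT confirmed only after Day 28, and the other five each have Day 28 DLT risk p. Counting it turns reopen into close if the other five have exactly 2 DLTs (maximum of 2 allowed), 10p²(1-p)³, or exactly 1 (maximum of 1 allowed), 5p(1-p)⁴.

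| p | Maximum 2 of 6 | Maximum 1 of 6 |
|---|---|---|
| 10% | 7% | 33% |
| 20% | 20% | 41% |
| 30% | 31% | 36% |
| 40% | 35% | 26% |

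These figures take the late DLT as given. Without that condition, let each subject have a Day 28 risk of 20% and a further late-only risk q. The probability of a changed decision is P(X ≤ c | 0.20) - P(X ≤ c | 0.20 + q), with X binomial on n = 6 and c the maximum allowed.

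| q | c = 2 | c = 1 |
|---|---|---|
| 2% | 2.6% | 4.9% |
| 5% | 7.1% | 12.1% |
| 10% | 15.7% | 23.5% |

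**5. The limit as a count.** Attainable rates are 0, 16.7, 33.3, 50% and up. 2/6 = 33.3% is above 33%, so the text closes the arm at 2 of 6. Exact binomial with n = 6:

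| True DLT rate | P(exactly 2) | Reopen if ≤1 of 6 | Reopen if ≤2 of 6 |
|---|---|---|---|
| 20% | 25% | 66% | 90% |
| 30% | 32% | 42% | 74% |

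**The case against.** **Safeguards at the gate.** Twenty-eight days is a minimum, and subjects enrolled earlier will have longer follow-up. The review takes in all available safety data, not only formal DLTs. Table 5.1-2 requires marrow of adequate recovery for the end-of-cycle assessment; if it has not recovered, it is repeated and the next cycle waits. A reader might infer that late marrow failure would be invisible at the gate. The documents do not support that, since it would normally be seen at about Day 28. What stands is that seeing it does not make it count: the resume rule is a percentage of DLTs.

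**Exposure.** A reader might infer that all 34 remaining subjects (40 - 6) could be randomized to 1000 mg with no further look. DMC Interim #2 comes at around 60 subjects, 20 per arm, after 2 months of treatment and follow-up. With balanced arms that is about 14 further subjects (20 - 6), plus any randomized meanwhile, and the first six should by then be at or near the 8-week mark. Individual hold and discontinuation rules also apply. None of this is tied to the first-six limit.

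**Weight of the evidence.** The 42-day Cycle 2 delay uses a neutrophil, platelet and blast definition that differs from the marrow DLT, so it is only weak evidence that this DLT is expected. Attribution to ulocuplumab and discussion with the Medical Monitor narrow what counts.

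**DMC Charter.** Protocol 7 and SAP 7.1 leave review details to it. It is not among the documents and may already cover a late-confirmed DLT.

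**Threshold.** The two inequalities leave no gap, so the rule is not undefined. A reader might infer that one third was meant and that 2 of 6 reopens the arm, because the protocol writes 4 of 6 as 66% and the escalation table accepts 1 of 3. The first is an efficacy result. The second is a planning table limited to the escalation cohort, and no observed DLT count is reported. Appendix 2 points the other way: its 3+3 comparator treats 2 of 6 as exceeding the MTD. That is not the gate's design either, so the intent is not settled.

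**Conclusion.** The timing point holds. Followed as written, the gate can reopen the 1000 mg arm on a count that omits DLTs listed in Protocol 5.3.1, and neither document provides for one confirmed afterwards. The day counts follow from the protocol alone. The frequency cannot be stated because no late-DLT rate is given; the probabilities in step 4 show sensitivity under assumed rates and are not forecasts. The safeguards reduce the risk without closing the gap.

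The threshold point is narrower. The present text closes the arm at 2 of 6. The request is to confirm and state that as a count, because exactly 2 of 6 is a likely result (25% to 32% at assumed DLT rates of 20% to 30%) and the two possible limits give very different chances of reopening.

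**What to change.** 1. Keep the 28-day gate. In Protocol 5.3.1 and SAP 2.2, state that the two hematologic criteria apply to toxicity arising from Cycle 1 dosing even if they are confirmed after Day 28.
2. In Protocol 8.5 and SAP 2.1 to 2.2, add that the 1000 mg arm is suspended again if a late-confirmed DLT among the first six takes the count over the limit.
3. Replace the percentage by a count: either ≤1 of 6 resumes and ≥2 of 6 closes (the present text), or, if one third was intended, ≤2 of 6 resumes and ≥3 of 6 closes.
4. If the DMC Charter already contains such rules, carry them into the protocol and SAP.

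The cost is a few sentences in each document. The first reopening is not delayed. The downside is a possible second pause, during which only the other two arms would randomize; some further subjects may also receive 1000 mg before a re-suspension.

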5.3.3 Other Assessments

- ECOG assessment ([Appendix 4](#))
- HCT-CI assessment ([Appendix 6](#))
- Physical Examination/Measurement
- Vital Signs
- ECG-safety ECGs will be done for all subjects at screening, during the treatment period and during follow-up as indicated in [Table 5.1-1](#), [Table 5.1-2](#), and [Table 5.1-3](#). Serial ECGs will be obtained only from a subset of subjects in the expansion cohort (a minimum of 15 subjects per dose level, Serial PK/ECG subset) as indicated in [Table 5.5.1-1](#).
- Concomitant Medications including Medical Treatment Procedures.

5.3.4 Additional Data to be Collected during Trial

Reasons for early discontinuation of any treatment cycle will be collected. This may include but not be limited to progression of cytopenias, lymphadenopathy, organomegaly, fever, weight loss, night sweats, fatigue, etc.

5.3.5 Imaging Assessment for the Study

Any incidental findings of potential clinical relevance that are not directly associated with the objectives of the protocol should be evaluated and handled by the Study Investigator as per standard medical/clinical judgment.

5.4 Efficacy Assessments

5.4.1 Primary Efficacy Assessment

Efficacy assessments will be determined by changes in bone marrow aspirate/biopsy, hematological laboratory tests, red blood cell transfusion dependency, and assessments for extramedullary disease (if applicable). Leukemia response assessment will be evaluated using AML IWG 2003 ([Appendix 1](#)).

The Time and Events Schedules ([Table 5.1-1](#), [Table 5.1-2](#), and [Table 5.1-3](#)) summarizes the frequency and timing of efficacy measurements.

Primary efficacy analyses will be based on the best overall response.

5.4.2 Secondary Efficacy Assessments

Duration of remission (DoR) and overall survival are secondary endpoints. Refer to [Section 8.3](#) for the definition of these endpoints. For OS, every effort should be made to collect survival date on all randomized subjects including subjects who withdraw from treatment for any reason, who

are eligible to participate in the study and who have not withdrawn consent for survival data collection. If the death of a subject is not reported every date collected in this study representing a date of subject contact will be used in determining the subject's last known alive date.

